Statistical Analysis Plan

Protocol Identification Number: S61792

Brief Title: Role of sleep on motor learning in Parkinson's disease and healthy older adults

Official Title: Boosting motor learning through sleep and targeted memory reactivation in Parkinson's disease and healthy older adults

Acronym: TARGET-SLEEP

Study type: Interventional

Principal Investigator: [name]

Note on protocol amendment 27 April 2021:

It was noted that a formal power calculation was not provided in the original submission on clinicaltrials.gov. The a-priori determined power calculation has now been added. Importantly, the target sample for recruitment did not change to what was noted on the original submission. Moreover, a change was made to the secondary outcomes 7 and 8 regarding dual tasking for experiment 2. It was decided to not have participants perform the dual-task condition during learning, as to minimize learning effects on the primary outcome. Importantly, due to COVID-19 restrictions, recruitment for experiment 2 had not yet commenced and hence no subjects had been randomized prior to submission of this protocol amendment.

Brief summary:

People with Parkinson's disease (pwPD) often present difficulty consolidating newly learned skills into long-term memory. Sleep facilitates motor memory consolidation in healthy adults, especially in combination with targeted memory reactivation (TMR). TMR works by adding associated sounds during learning that are replayed during sleep and thus reinforce the recently formed neural connections. Importantly, recent work suggested that consolidation during sleep may be preserved in pwPD, but robust findings are lacking and have not involved TMR. The objective of the present study is to address this imperative question by investigating the effect of napping on motor memory consolidation by experimentally manipulating exposure to sleep (Experiment 1) and TMR (Experiment 2) for the first time. Concretely, the investigators will first compare the effect of a 2-hour nap to that of a wake control period in pwPD and healthy age-matched controls. A validated motor sequence learning task will be used to test for behavioral markers of motor learning and polysomnography with electroencephalography (EEG) will be conducted to study the neural correlates of sleep-related motor learning effects. In a second experiment, the investigators will then test the effects of adding TMR during post-learning sleep, by comparing performance on two motor sequences of which only one is reactivated during post-learning napping using auditory TMR.

Primary outcome:

Experiment 1: Participants perform a self-initiated MSL task by tapping a five-element finger sequence presented on screen as rapidly and accurately as possible with their non-dominant hand for 18 blocks during learning, immediately after the nap or wake intervention (Retest 1) and again 24hours

later without further practice (Retest 2). Each block consists of 50 key presses (ideally 10 sequences) and is followed by a rest block of 15-20 seconds without finger tapping. A two-minute rest period will be implemented after 14 blocks to further minimize the effects of fatigue on the last 4 blocks that are used to calculate the primary outcome. Performance on the MSL will be assessed using the 'Performance Index (PI)' [$PI = \exp^{-(\text{seqDur}(x))} * \exp^{-(\text{Errors}(x)/12)} * 100$], whereby (x) represents the blocks of the trials (King et al. 2017b). Given that both speed and accuracy determine the PI, these measures will be explored. During the single-task condition, participants view a fixation cross in the middle of the screen with the sequence presented above.

The primary outcome for experiment 1 will be the offline consolidation, measured as the change in PI between the first 4 blocks at Retest 1 immediately after the nap or wake intervention and the last 4 blocks of Learning immediately prior to the intervention. The primary outcome for experiment 1 will be analyzed with a repeated measures analysis of variance with the following factors and conditions: 4 blocks * 2 sessions (end of learning/begin of retest 1) * 2 groups (nap/wake) * 2 populations (pwPD/controls). Linear mixed models will be considered depending on the presence of missing values and interactions with covariates (age, gender, disease severity and levodopa equivalence dose) will be analyzed.

Experiment 2: The design of experiment 2 is similar to experiment 1, except that participants will learn two motor sequences that are visually and auditory cued by means of a serial reaction time task (SRT). After learning both sequences, participants will nap for 2 hours, but this time while the melody of one of the two sequences will be replayed using auditory TMR. Performance on both sequences will be re-assessed immediately after the intervention (Retest 1), and again at 24h retention (Retest 2) without cues.

The primary outcome for experiment 2 is the 'offline consolidation' defined as the change in PI between the first 4 blocks at retest immediately after the nap and the last 4 blocks at learning prior to the intervention, which will be compared between the sequence that was replayed during the nap (replay) and the sequence that was not replayed (no-replay). The primary outcome for experiment 2 will be analyzed with a repeated measures analysis of variance with the following factors and conditions: 4 blocks * 2 sessions (end of learning/begin of retest 1) * 2 sequences (replay/no-replay) * 2 groups (pwPD/controls). Linear mixed models will be considered depending on the presence of missing values and interactions with covariates (age, gender, disease severity and levodopa equivalence dose) will be analyzed.

Secondary outcomes

All other comparisons for experiments 1 and 2 are considered secondary in importance. The PI is used as the main dependent variable of interest for all secondary outcomes listed below, which will be compared across the two intervention groups (Nap/Wake) and two study populations (pwPD/Controls). An MSL with consecutive dual task condition is performed for an additional 4 blocks at learning, immediately after the intervention (Retest 1) and again after

24hrs of retention (Retest 2). The following comparisons will be analyzed for both experiments.

Single task performance (PI):

1. Retention, measured as the change in PI between the first 4 blocks at Retest 2 compared to the last 4 blocks at Retest 1.
2. Learning slope over 14 blocks during learning, prior to the intervention.
3. Learning slope over 14 blocks after the 24hr retention period (Retest 2)
4. End of learning performance assessed over the last 4 blocks during learning prior to the intervention (Learning)
5. Post-extensive practice performance assessed over the last 4 blocks immediately after the intervention (Retest 1)

Dual tasking performance (PI):

1. Offline consolidation measured as the change in PI between the 4 blocks of dual tasking at Retest 1 immediately after the intervention compared to the 4 blocks of dual tasking during learning for experiment 1, and differences on PI between sequences A and B during the 4 blocks at Retest 1 for experiment 2.
2. Retention, measured as the change in PI between the 4 blocks of dual tasking at Retest 2 compared to the 4 blocks of dual tasking at Retest 1 for experiment 1, and differences on PI between sequences A and B during the 4 blocks at Retest 2 for experiment 2.
3. Learning performance over the 4 blocks of dual tasking during learning prior to the intervention for experiment 1 only.
4. Learning performance over the 4 blocks of dual tasking immediately after the intervention (Retest 1) for both experiments.
5. Learning performance over the 4 blocks of dual tasking after the 24hr retention period (Retest 2) for both experiments.

Dual task cost (Δ PI), i.e. the difference in PI between 4 blocks of dual tasking and 4 blocks of single tasking.

1. Offline consolidation measured as the change in Δ PI between Retest 1 immediately after the intervention (4 blocks of dual tasking versus last 4 blocks of single tasking) and the Δ PI during learning (4 blocks of dual tasking versus the first 4 blocks of single tasking) for experiment 1, and difference in Δ PI between sequences A and B (4 blocks of dual tasking versus last 4 blocks of single tasking) at Retest 1 for experiment 2.
2. Retention, measured as the change in Δ PI between Retest 2 (4 blocks of dual tasking and last 4 blocks of single tasking) and Retest 1 (4 blocks of dual tasking and last 4 blocks of single tasking) for experiment 1, and difference in Δ PI between sequences A and B (4 blocks of dual tasking versus last 4 blocks of single tasking) at Retest 2 for experiment 2.
3. Learning performance assessed as the Δ PI of the 4 blocks of dual tasking and first 4 blocks of single tasking during learning for experiment 1 only.
4. Post extensive practice assessed as the Δ PI of the 4 blocks of dual tasking and last 4 blocks of single tasking immediately after the intervention (Retest 1) for both experiments.

5. Post extensive practice assessed as the Δ PI of the 4 blocks of dual tasking and last 4 blocks of single tasking after the 24hours retention period (Retest 2) for both experiments.

Control comparisons (PI): For experiment 2, four additional comparisons will be analyzed to ensure that participants could learn both sequences equally well. The two sequences can be labeled as either (sequence A / sequence B), irrespective of which sequence was replayed during the nap period, or as (replay / no-replay) respective of the sequence that was replayed during the nap period.

1. End of learning performance on sequence A and B will be assessed as the difference in PI between the last 4 blocks of sequence A and the last 4 blocks of sequence B during learning prior to the intervention.
2. Learning slopes of sequence A and B will be assessed as the difference in PI between the first 14 blocks of sequence A and the first 14 blocks of sequence B during learning prior to the intervention.
3. End of learning performance on the replay and no-replay sequences will be assessed as the difference in PI between the last 4 blocks of the TMR sequence and the last 4 blocks of the control sequence during learning prior to the intervention.
4. Learning slopes of the replay and no-replay sequences will be assessed as the difference in PI between the first 14 blocks of sequence A and the first 14 blocks of sequence B during learning prior to the intervention.

Tertiary outcomes

Experiment 1 - Motor Execution Test (MET)

Participants perform a self-initiated MET by tapping a simple 4-element (i.e. 4-3-2-1) finger sequence presented on screen as rapidly and accurately as possible with their non-dominant hand for 4 blocks during learning and again for 4 blocks at each retest assessment. Each block consists of 52 key presses (ideally 13 sequences) and is followed by a rest block of 15-20 seconds without finger tapping. Performance on the MET will be compared between Retest 1 and learning and between Retest 2 and Retest 1.

Experiment 2 - Random Serial Reaction Time task (random SRT)

Participants will perform random sequences that are visually cued by means of a SRT for 4 blocks at learning and again at each retest assessment. Each block consists of 50 key presses and is followed by a rest block of 15-20 seconds without finger tapping. Performance on the random SRT will be compared between Retest 1 and learning and between Retest 2 and Retest 1.

Psychomotor Vigilance Test (PVT):

The MSL (Experiment 1) and SRT (Experiment 2) tests will be preceded by a 10-minute PVT as an objective measure of the participants' vigilance prior to testing. The PVT will be presented on a laptop and subjects will be instructed to press a button as quickly as possible each time a visual stimulus is presented in the middle of the screen. Changes in PVT performance (number of lapses in attention defined as response times \geq twice the median response time) will be

assessed between Retest 1 and the period prior to the intervention (i.e. Learning), as well as between Retest 2 and Retest 1.

Planned data exclusion

Anticipated data exclusion criteria are the performance measures of the first block after each NAP/WAKE or 24-hour Retention period, given these may be confounded by start-up effects. We will perform a sensitivity analysis without these trials to control for these confounding effects.

Power calculation

Based on the findings by Terpening et al. (2013) and Dan et al. (2015), a minimum of 16 subjects per group (NAP, WAKE) will be required according to our power analysis based on the MSL-outcomes using $\beta=0.20$ and $\alpha=0.05$ to detect a significant group difference. To account for potential dropouts, the recruitment target is set 20% higher to ensure adequate power in our final analysis. As such, a total of 40 PD patients and 40 healthy elderly controls will be recruited for experiment 1 (i.e. 20 in each NAP/WAKE group). The best sample estimation at this time for experiment 2 is based on previous TMR studies in younger adults also recruiting 16 subjects per nap/wake group (Antony et al. 2012). Therefore, we will target to recruit a total of 20 PD and 20 healthy elderly controls for Experiment 2, again accounting for 20% potential dropout.

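### Optional efficiency gain: both primary analyses test raw change in PI; adjusting the nap and replay contrasts for end-of-learning PI is at least as precise in large samples

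*SAP*

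**What the plan says.** Under Primary outcome, the SAP defines offline consolidation in Experiment 1 as "measured as the change in PI between the first 4 blocks at Retest 1 immediately after the nap or wake intervention"; the comparator is the final 4 learning blocks. The model is a repeated measures ANOVA with factors "4 blocks * 2 sessions (end of learning/begin of retest 1) * 2 groups (nap/wake" and population (pwPD or controls). Experiment 2 has the same outcome, compared between the replayed and non-replayed sequence, with factors "4 blocks * 2 sessions (end of learning/begin of retest 1) * 2 sequences (replay/no-replay" and population.

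Mixed models are only to be considered, depending on missing values. The covariate statement, the same in both experiments, is that "interactions with covariates (age, gender, disease severity and levodopa equivalence dose) will be analyzed". End-of-learning PI is not in that list. It appears as a secondary outcome and, for Experiment 2, among the control comparisons: "End of learning performance on the replay and no-replay sequences will be assessed as the difference in PI".

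The Brief summary describes the design as "experimentally manipulating exposure to sleep (Experiment 1) and TMR (Experiment 2". Randomisation is mentioned only in the amendment note, which says that "recruitment for experiment 2 had not yet commenced and hence no subjects had been randomized". The SAP does not describe how the replayed sequence is assigned.

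**The concern.** With end of learning and Retest 1 as the two levels of session, the nap effect is the session x group term and the replay effect is the session x sequence term. Averaged over blocks, each is a comparison of mean raw change. Raw change subtracts the whole of any chance difference in end-of-learning PI, whereas the part that carries over to Retest 1 is rho x k, with rho the correlation between the two sessions and k = SD(Retest 1)/SD(end of learning). With equal SDs the change score over-corrects by a fraction 1 - rho.

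Under random allocation this causes no bias. What is at stake is precision, using a pre-intervention measurement that the trial already collects. It matters most for nap x population: the Brief summary asks whether consolidation during sleep is preserved in pwPD, while the Power calculation sizes only on a nap/wake group difference.

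**Working it through.** **The plan's own figure.** The Power calculation gives a minimum of 16 per nap/wake group at alpha 0.05 and power 0.80, raised for 20% dropout. 16/(1 - 0.20) = 20, so 20 per group and 40 per population reproduce. The 16 cannot be reproduced, because no effect size or SD is stated. Solving backwards (two-sided 5%, t-test, 16 v 16) gives a standardised difference of 1.024. I take this, as an assumption, to be the effect on change in PI.

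**Variance.** In units of the end-of-learning variance, per person:

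- raw change: 1 + k² - 2·rho·k
- adjusted: k²(1 - rho²)
- the first minus the second: (1 - rho·k)²

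The difference is never negative and is zero only when rho·k = 1. At k = 1 the ratio adjusted/change is (1 + rho)/2.

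**Range for k.** PI is exponential in sequence duration. If duration is in seconds (the SAP states no unit) and everyone shifts equally, a 0.1 s speed-up multiplies PI and its SD by exp(0.1), about 1.1; 0.2 s gives about 1.2; a 0.1 s slowing gives about 0.9. Hence k from 0.9 to 1.2.

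Large-sample variance ratio, adjusted/change:

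| k | rho 0.5 | 0.7 | 0.8 | 0.9 | 0.95 |
|---|---|---|---|---|---|
| 0.9 | 0.67 | 0.75 | 0.79 | 0.81 | 0.79 |
| 1.0 | 0.75 | 0.85 | 0.90 | 0.95 | 0.975 |
| 1.1 | 0.82 | 0.92 | 0.97 | 1.00 | 0.98 |
| 1.2 | 0.87 | 0.97 | 1.00 | 0.98 | 0.88 |

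**Power of the planned change analysis** (noncentral t, effect 1.024, n per cell):

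| Contrast | Noncentrality | n = 16 | n = 20 |
|---|---|---|---|
| Nap within one population, two-sample | 1.024·√(n/2) | 0.800 | 0.884 |
| Nap x population, effect in one population only | 1.024·√(n/4) | 0.522 | 0.618 |
| Nap pooled, effect in both populations | 1.024·√n | 0.981 | 0.995 |

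The within-population contrast is not named as a primary test; it is shown because the sample size rests on it. With the error degrees of freedom of all four cells it has about 0.89 at 20 per cell.

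**Power after adjustment, Experiment 1.** Simulation, 10,000 runs per setting, four cells, one slope per population; Monte Carlo SE about 0.3 to 0.5 points. Entries are change → adjusted, in %.

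| Setting | rho 0.5 | 0.7 | 0.8 | 0.9 | 0.95 |
|---|---|---|---|---|---|
| Nap x population, 20 per cell, k = 0.9 | 60.8 → 78.4 | 61.4 → 73.0 | 61.7 → 71.0 | 61.6 → 69.3 | 61.6 → 71.1 |
| same, k = 1 | 62.2 → 73.1 | 61.7 → 67.3 | 61.8 → 65.4 | 61.8 → 62.6 | 62.3 → 62.4 |
| same, k = 1.1 | 62.2 → 69.5 | 61.8 → 63.7 | 62.1 → 61.9 | 61.0 → 59.7 | 61.6 → 60.6 |
| same, k = 1.2 | 61.7 → 66.6 | 61.9 → 62.0 | 62.8 → 61.4 | 61.7 → 61.6 | 61.5 → 65.8 |
| Nap x population, 16 per cell, k = 1 | 51.6 → 62.6 | 51.8 → 57.4 | 52.2 → 55.8 | 52.1 → 53.3 | 51.9 → 51.9 |
| Nap within population, 20 per cell, k = 1 | 89.5 → 95.6 | 89.2 → 92.7 | 89.2 → 91.4 | 89.0 → 89.6 | 89.3 → 89.2 |

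The adjusted test rejected a true null in 4.8 to 5.1% of runs at 20 per cell.

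**Experiment 2.** Here rho and k refer to the within-person replay minus no-replay difference. The SAP gives no effect size. I assume a standardised difference in change of 0.512 (half of 1.024), which gives 80% power with 32 people. At 20 per population, power moves as follows:

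| k | rho 0.5 | 0.7 | 0.8 | 0.9 | 0.95 |
|---|---|---|---|---|---|
| 1.0 | 88.9 → 95.1 | 88.7 → 92.4 | 88.6 → 90.6 | 89.0 → 89.8 | 89.0 → 88.8 |
| 1.1 | 88.5 → 93.2 | 88.0 → 89.9 | 88.2 → 88.1 | 87.8 → 87.1 | 88.4 → 88.0 |

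**The case against.** The plan is coherent as it stands: the outcome is change, the ANOVA tests change, and under random allocation the test is valid. Preferring adjustment is therefore a recommendation and not a correction. That stands, and the point is put no higher.

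The advantage is a large-sample one, and the trial has 16 to 20 per cell. This also stands. When rho x k is near 1 there is no gain or a small loss: at k = 1.1 and rho 0.9, nap x population falls from 61.0% to 59.7%. PI averages 4 blocks of 50 key presses on either side of a 2-hour interval, so a high rho is plausible; at k = 1 and rho 0.9 or more the gain is then under 1 point. The largest gains need a low rho or a smaller SD at Retest 1.

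The pooled nap test has almost nothing to gain, and the interaction scenario (effect in one population only) is not the one the plan sizes on. Both are true. The interaction is nevertheless a term of the planned model and bears on the stated question.

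In Experiment 2 the benefit depends on random or counterbalanced choice of the replayed sequence, which the SAP does not describe, and the effect size used here is assumed. The planned control comparison examines the end-of-learning difference between sequences but does not use it to sharpen the replay contrast.

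**Conclusion.** The point holds as an optional improvement of low weight. Both primary analyses test raw change, and end-of-learning PI is a covariate in neither. Under random allocation both approaches are unbiased, and adjustment is never less precise in large samples.

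At the planned size, the change in power for nap x population runs from a loss of about 1.4 points (k = 1.2, rho 0.8) to a gain of about 18 points (k = 0.9, rho 0.5). At k = 1 the gain is about 11 points at rho 0.5, 4 at 0.8 and none at 0.95. These figures rest on assumed values of rho and k and on the back-solved effect.

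The point concerns only the nap and replay contrasts. The pwPD v control comparison is not randomised, and adjusting it for end-of-learning PI would change the question asked.

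**What to change.** Before the relevant data are analysed, state the following in the SAP.

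- **Experiment 1:** estimate the nap contrasts from mean PI over the first 4 Retest 1 blocks, with terms for group, population, group x population and end-of-learning PI (mean of the last 4 learning blocks, centred within population, with its own slope in each population).
- **Experiment 2:** regress the within-person replay minus no-replay difference at Retest 1 on the same difference at end of learning, with population coded -1/2 and +1/2. Leave the covariate uncentred, so that the intercept is the replay effect at zero end-of-learning difference; the population term is replay x population.
- **Both:** keep the change-score ANOVA for the session, block and pwPD v control terms, and as a sensitivity analysis for nap and replay. Say which model decides which contrast.

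The amendment note confirms only that Experiment 2 had not begun. If Experiment 1 data have already been analysed, leave the planned ANOVA deciding there and report the adjusted nap contrasts as a sensitivity analysis.

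The cost is SAP wording, with no new data. Adjustment uses two degrees of freedom in Experiment 1 and one in Experiment 2, about 1 to 1.5 points of power when rho x k is near 1. Two models are then reported for one primary outcome, which is why the deciding model must be named.

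### Does naming disease severity and levodopa dose as covariates damage models that also contain healthy controls?

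*SAP*

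**What the plan says.** Under Primary outcome, the Experiment 1 analysis is a repeated measures ANOVA with factors "4 blocks * 2 sessions (end of learning/begin of retest 1) * 2 groups (nap/wake) * 2 populations (pwPD/controls". The Experiment 2 model replaces nap/wake by a within-person factor and keeps population: "2 sequences (replay/no-replay) * 2 groups (pwPD/controls". Neither list of factors contains a covariate.

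In each experiment the next sentence allows a switch to linear mixed models if values are missing, and adds that "interactions with covariates (age, gender, disease severity and levodopa equivalence dose) will be analyzed". It gives no value for controls, no centring rule and no list of the factors with which each covariate interacts. It also does not say that all four covariates enter one model.

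Under Power calculation, "a minimum of 16 subjects per group (NAP, WAKE) will be required". The recruitment targets are "a total of 40 PD patients and 40 healthy elderly controls will be recruited for experiment 1" and "a total of 20 PD and 20 healthy elderly controls for Experiment 2".

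**The concern.** Healthy controls have no Parkinson's severity and, by inference, no levodopa dose. If these two covariates are put into a model with both populations, software needs a value for controls, and the obvious choices look bad.

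- **Left missing:** complete-case fitting removes all controls, and population can no longer be estimated.
- **Set to 0 without centring:** the nap (or replay) coefficient and its interaction with population describe a patient with zero severity and zero dose, outside the sample. Their standard errors can be much larger than in the model without covariates.

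If those coefficients were set beside the ANOVA, a loss of significance might be taken for a real effect of adjustment when it came only from the coding. Nap versus wake is also the contrast on which the sample size is based, so the matter seems to touch the main question of Experiment 1.

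**Working it through.** **The plan's own figure.** The step from 16 to 20 per group reproduces: 16/(1 − 0.20) = 20, and 16 × 1.2 = 19.2, rounded up to 20. The 16 itself cannot be reproduced, because the SAP gives no effect size or SD. The SAP states no standard error for the covariate analysis.

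**Set-up.** Reduce Experiment 1 to one change score per person, start of Retest 1 minus end of learning. Let G be nap/wake, P the indicator for pwPD, and x a disease covariate with x = 0 in controls. The joint model has the terms 1, G, P, GP, x and Gx. Experiment 2 has the same structure with each person's replay-minus-no-replay difference as outcome; there the replay × covariate interaction is the slope on x.

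**Step 1: does coding alter the interaction test?**
- Centring on any constant k: G(x − k) = Gx − kG. G is already in the model.
- Centring within pwPD at mean m, controls 0: G(x − mP) = Gx − mGP. GP is already in the model.

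Both recodings span the same column space, so the Gx coefficient, its standard error and its p-value do not change. A fit to simulated data with both covariates (20 per cell, assumed distributions) showed this. The nap × severity estimate was 0.0419, SE 0.0201, p = 0.040 under all three codings.

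**Step 2: does dropping controls alter it?** In controls x is constant, and G, P and GP already fit the two control cell means exactly. The slope on Gx therefore comes from pwPD alone, with or without controls in the data. Only the residual variance and its degrees of freedom differ. With one covariate and the full recruited sample these are 80 − 6 = 74 in the joint model and 40 − 4 = 36 in pwPD only. After dropping controls the nap × population design has rank 2 of 4, so population terms are lost from that fit. They remain available in the ANOVA, which has no covariates.

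**Step 3: what does change?** Let r be the mean/SD of the covariate in pwPD (not in the SAP; assume 1.5 to 4). Let V be the variance of the effect within one population, taken as equal in both. In pwPD the effect at x = 0 has variance V(1 + r²); in controls it is V.

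| Coefficient, one covariate | SE ratio to model without covariate | r = 1.5 | r = 4 |
|---|---|---|---|
| Nap or replay, effect coding, uncentred | √(1 + r²/2) | 1.46 | 3.00 |
| Nap or replay, pwPD as reference, uncentred | √(1 + r²) | 1.80 | 4.12 |
| Nap or replay, controls as reference, uncentred | 1 | 1.00 | 1.00 |
| Interaction with population, uncentred or grand-mean centred | √(1 + r²/2) | 1.46 | 3.00 |
| Nap or replay, effect coding, grand-mean centred | 1 | 1.00 | 1.00 |
| All of these, centred within pwPD | about 1 | 1.00 | 1.00 |

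With both covariates together (severity r of 1.5 to 4, dose r of 1.5 to 2.5, correlation 0.4, all assumed), simulated designs gave 1.7 to 3.4 under effect coding.

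The larger standard errors belong to a different quantity, an effect extrapolated to zero severity and zero dose. The nap effect at the pwPD mean, in controls, or averaged over both can be recovered from the same uncentred fit with the same standard error as in the centred fit. No information is lost.

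**The case for a change.** The best case for a change is that the covariate sentence is attached to both primary outcomes and leaves a choice that could be made after the data are seen. Grand-mean centring, a common default, restores the nap or replay main effect but leaves the interaction with population inflated, so a careful analyst could still be caught. If all four covariates went into a single complete-case model, the age and gender interactions would also lose 40 of 80 or 20 of 40 participants. One sentence per experiment would settle all this at almost no cost.

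What stands is that the text is silent, and that the nap × population or replay × population coefficient should not be read from a joint model with zero-coded disease covariates unless they are centred within pwPD. The rest needs steps that the SAP does not take. It writes no single model with all four covariates and no zero coding, and it does not say that nap, replay or population effects will be taken from the covariate model or compared with the ANOVA. A loss of power cannot be attached to the point either: it would need an assumed coding, assumed covariate distributions and an assumed starting power for a coefficient the SAP does not designate for testing.

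**Conclusion.** The concern does not call for a change. The SAP leaves unwritten that disease severity and levodopa dose are examined within pwPD. That is the only reading under which these covariates have meaning, and it is the one an analyst would adopt. The primary ANOVA is untouched. The announced interaction tests are identical under the three centring choices, and leaving controls out gives the same slope estimates with a different residual variance and fewer degrees of freedom. The inflation, from 1.0 to above 4, is confined to coefficients the SAP assigns no role in this analysis, and its size depends on means, SDs and coding that the SAP does not give.

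This rests on three readings: that the covariate interactions supplement the ANOVA and do not replace it as the source of the nap and replay effects; that the nap × population term (in Experiment 2, the population term for the replay difference) stays in any joint model; and, for the equality of the joint and pwPD-only slopes, that age and gender slopes pooled over both populations are not in the same model. With such pooled slopes the two fits could differ somewhat, but the invariance to centring in Step 1 would still hold. A clarifying sentence would do no harm, but no announced result depends on it.

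### The Experiment 2 primary model omits the order in which the two sequences are tested, which costs precision and leaves any chance imbalance in order uncorrected

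*SAP*

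**What the plan says.** In the SAP's Primary outcome section, every Experiment 2 participant learns two sequences and then naps while the melody of one is replayed. After that, "Performance on both sequences will be re-assessed immediately after the intervention (Retest 1") and again at 24 hours. The outcome for each sequence is "the change in PI between the first 4 blocks at retest immediately after the nap and the last 4 blocks at learning", compared between the replayed and the non-replayed sequence.

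The model is a repeated measures ANOVA of 4 blocks × 2 sessions × "2 sequences (replay/no-replay) * 2 groups (pwPD/controls"). Linear mixed models are held in reserve for missing values, and "interactions with covariates (age, gender, disease severity and levodopa equivalence dose) will be analyzed". Test order is neither a factor nor a listed covariate.

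The same SAP treats position within a session as something that affects performance:

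- Planned data exclusion names "the performance measures of the first block after each NAP/WAKE or 24-hour Retention period, given these may be confounded by start-up effects".
- The Experiment 1 task description, to which Experiment 2 is said to be similar, places a two-minute rest before the last 4 blocks to limit fatigue.

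The four control comparisons for Experiment 2 (Secondary outcomes) all concern performance during learning. None looks at order at retest.

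**The concern.** The replay effect is a within-person comparison of two sequences tested in the same session. One sequence must be tested before the other, so start-up, fatigue or interference tied to position can separate the two changes for reasons unrelated to replay. In a paired two-condition design, order is normally a model term for that reason.

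Two things are at stake:

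- **Balanced order.** The order effect pushes the paired difference up in half the participants and down in the other half. The average is untouched, but the spread is charged to error and power is lost.
- **Order unbalanced by chance.** Part of the order effect passes into the estimated replay effect, and the model has no term to remove it.

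This holds whatever the protocol says about counterbalancing, because it concerns the model terms that the SAP does fix.

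**Working it through.** **Inputs from the SAP.** Power calculation gives 16 per group before dropout and a recruitment target of 20 PD and 20 controls for Experiment 2. The target follows from the 16: 16/(1 − 0.20) = 20, and 16 × 1.2 = 19.2, rounded up to 20. The 16 itself cannot be reproduced, since no effect size or SD is given, but nothing below depends on it. The check uses 2 × 16 = 32 completers.

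**Assumed inputs.** The SAP gives no order effect. Let o be the amount by which the later-tested sequence's change in PI exceeds the earlier-tested one's, in SDs of the paired (replay minus no-replay) difference. The range used is o = 0.25, 0.5 and 1.0. Let f be the share of participants whose replayed sequence is tested first at Retest 1.

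**Step 1: effect on the estimate.** The paired difference is τ − o when the replayed sequence comes first and τ + o when it comes second. Its mean is τ − (2f − 1)o, so the bias has size |2f − 1| × o:

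- f = 0.5: zero.
- f = 0.625 (20 of 32): 0.25 × o = 0.0625, 0.125 and 0.25 SD.
- f = 0.75 (24 of 32): 0.5 × o = 0.125, 0.25 and 0.5 SD.
- f = 1: the whole of o, and no model can separate order from replay.

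**Step 2: effect on precision when f = 0.5.** Without an order term the SD in the test is about √(1 + o²) = 1.031, 1.118 and 1.414. With 32 completers, 80% power in the absence of an order effect corresponds to a standardised paired effect of 0.511, and 0.511 × √32 = 2.89. The two-sided 5% critical value (31 df) is 2.04. Multiplied by the three SDs it becomes 2.10, 2.28 and 2.88. Approximate power is then Φ(2.89 − 2.10) = 0.79, Φ(2.89 − 2.28) = 0.73 and Φ(2.89 − 2.88) = 0.50, against Φ(2.89 − 2.04) = 0.80 with no order effect.

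**Step 3: simulation.** Paired t-test, n = 32, 20,000 runs per cell:

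| | o = 0.25 | o = 0.5 | o = 1.0 |
|---|---|---|---|
| Power, f = 0.5, no order term | 0.78 | 0.73 | 0.51 |
| Power, f = 0.5, with order term | 0.80 | 0.80 | 0.80 |
| Type I error, f = 0.5, no order term | 0.044 | 0.028 | 0.006 |
| Type I error, f = 0.625, no order term | 0.053 | 0.069 | 0.087 |
| Type I error, f = 0.75, no order term | 0.10 | 0.22 | 0.55 |

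With the order term, type I error lies between 0.047 and 0.052 for f = 0.5, 0.625 and 0.75.

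**Step 4: how likely is imbalance?** If order were assigned by simple randomisation (an assumption), the chance that |2f − 1| is at least 0.25 is 22% with 32 participants and 15% with 40.

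**Step 5: the start-up exclusion.** Suppose the rule removed one block per session, from the first-tested sequence only. The mean block position would be (2 + 3 + 4)/3 = 3.0 for that sequence and (1 + 2 + 3 + 4)/4 = 2.5 for the other. With a gain of b per block, the replay contrast in the sensitivity analysis would move by (2f − 1) × 0.5b, which is again zero at f = 0.5. A start-up loss s confined to block 1 affects the full four-block mean by s/4.

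**The case against.** The strongest reply is that test order, interleaving and counterbalancing are design matters usually left to the protocol, which is not shown, so the SAP's silence on them is no fault. That stands, and the point does not rest on it. The SAP also labels the sequences both as A/B and as replay/no-replay, and its amendment note speaks of randomisation in Experiment 2. Both suggest that the replayed sequence varies between participants. This is an inference, and it concerns which sequence is replayed more than which is tested first. Balance would remove the expected bias but not the loss of precision.

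Second, the outcome is a change from learning, so a position effect of equal size in both sessions cancels. A 10-minute vigilance test also precedes the motor task, so tapping does not begin straight from waking. Both are fair. The o used here is only what remains after cancellation, and it may be small. At o = 0.25 the cost is about 2 percentage points of power.

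Third, a reader might infer that the start-up rule strips a block from one sequence only, leaving blocks 2–4 of one against blocks 1–4 of the other. The SAP does not establish that:

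- The primary window is also written without saying per sequence, yet it can only mean the first 4 blocks of each, so the exclusion may carry the same meaning.
- "Participants will perform random sequences that are visually cued by means of a SRT for 4 blocks at learning and again at each retest assessment". If those blocks come first at retest, the literal first block belongs to neither sequence.
- The rule is applied outside the primary estimate: "We will perform a sensitivity analysis without these trials to control for these confounding effects".

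What is left of this part is an ambiguity worth one clarifying phrase.

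**Conclusion.** The omission of test order from the Experiment 2 primary model is a real but correctable weakness. With balanced order it costs precision: power at 32 completers falls from about 0.80 to 0.78, 0.73 and 0.51 for assumed order effects of 0.25, 0.5 and 1.0 SD, and the test becomes conservative. With chance imbalance the estimate shifts by |2f − 1| times the order effect.

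It is tempting to go further and say that the planned analysis biases the replay effect. The document does not support that. Bias needs order to be unbalanced across replay status, and nothing in the SAP shows that it is. All order effects used here are assumptions, and the largest loss needs an effect of a full SD. The case for a change rests on its low cost and on the SAP's own expectation of start-up and fatigue effects.

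**What to change.** In the Experiment 2 primary model, do one of the following:

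- Add test order (replay-first or no-replay-first at Retest 1) as a between-participant factor with its interactions with sequence and session. It cannot be a crossed within-participant factor in the planned ANOVA, because each participant has only one pairing of position with replay status at Retest 1.
- Fit a linear mixed model with position (first/second) and position × session, which also allows the order at learning to differ from the order at Retest 1.

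Either costs 1–2 df and no new measurement, provided block order is recorded (an assumption, as the SAP does not say so). Neither separates order from replay unless order varies between participants, so the SAP should state, or point to, how order is assigned.

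As a minor clarification, word the start-up sensitivity exclusion for Experiment 2 as the first block of each sequence at each retest, so that both sequences keep the same blocks. This is one phrase.
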